9.3.2 Data to be collected

In addition to the primary endpoints listed above, the following data will also be collected or derived from collected data:

- Participant unique anonymized identifier (study identification number);
- Relevant maternal baseline characteristics (See Appendix 5 for details);
- Other maternal data: type of conception (e.g., natural, in-vitro fertilization), date of LMP and EDD;
- Characteristics of prenatal care (See Appendix 5 for details);
- Characteristics of CYD-TDV exposure: dates doses administered, number of doses, dose intervals, and timing of pregnancy exposure;
- Offspring data: sex, length, weight, breastfeeding history.

9.4 DATA SOURCES

Seven data sources will be used for this study and these are described below. The primary data sources will include:

- (i) *Structured questionnaire*: To be used to ascertain self-reported socio-demographic information, medical history, medication and vaccination histories, use of recognized teratogenic substances (e.g., alcohol), maternal AEs, pregnancy outcomes, neonatal and infant outcomes.
- (ii) *Medical record review* (incl., prenatal care booklet, hospitalizations and primary health care records or other settings where antenatal care took place). To be used to supplement and verify self-reported information.

Secondary data sources will include:

- (iii) *SI-PNIEAPV*: Brazil's national vaccination spontaneous adverse event following immunization mandatory reporting system database. This database captures cases of pregnancy exposure, even in the absence of an AE, and contains the women's nominal data and CNS. This database will be used to identify pregnant women exposed to CYD-TDV in the private and public health care sectors (i.e., potential study participants) and to obtain contact information for these women.

In Brazil, the SI-PNI AEPV database is administered by the MoH and it is possible to have access to all data for a specific study following a specific request and approval from the appropriate local ethics committee. Data access may be requested via the State Department of Health of Paraná.

- (iv) *SISPRENATAL*: Brazil's national, public health care sector longitudinal database created by the MoH. It includes information on the first and subsequent antenatal visits, and puerperium visits taking place in the public health care sector, in addition to information on laboratory tests, ultrasounds and recommended maternal vaccinations. SISPRENATAL captures women's CNS number but not their nominal data. This database will be used to supplement and verify pregnancy related outcomes and provide SAE background rates for the safety analysis depending on availability.

In Brazil, SISPRENATAL is administered by the MoH and it is possible to have access to all the data for a specific study following a specific request and approval from the appropriate local ethics committee. Data access may be requested via the State Department of Health of Paraná.

- (v) *Paraná State Immunization registry*: This state-level database captures information on CYD-TDV vaccinations administered during public vaccination campaigns. CNS numbers are not systematically recorded in the registry; hence, data will be retrieved using probabilistic linkage. This database will be used to confirm the dates of CYD-TDV vaccination.

The DoH of Paraná administers this database and it is possible to have access to all data for a specific study following a specific request and approval from the appropriate local ethics committee. Data access is requested via the State Department of Health of Paraná.

- (vi) *SINASC*: Brazil's national live birth registry database. This database includes information on some maternal risk factors, delivery conditions, baby's condition at birth and presence of malformations. SINASC will be used to supplement and verify self-reported delivery, birth and neonatal outcomes, and to provide population-level AE background rates (i.e., external unvaccinated comparator data) for the safety analysis.

In Brazil, SINACS is administered by the MoH and it is possible to have access to all data for a specific study following a specific request and approval from the appropriate local ethics committee. Data access may be requested via the State Department of Health of Paraná.

- (vii) *SIM*: Brazil's national mortality database. This database captures information on causes of death, as well as maternal and infant demographics. It will be used to supplement and verify maternal, neonatal and infant deaths.

In Brazil, SIM is administered by the MoH and it is possible to have access to all data for a specific study following a specific request and approval from the appropriate local ethics committee. Data access may be requested via the State DoH of Paraná.

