9.2.5 Eligibility criteria

9.2.5.1 Inclusion criteria

- CYD-TDV exposed pregnant women of any age residing in the 30 municipalities of Paraná where public vaccination campaigns have been offered at the time of their pregnancy exposure, and whose pregnancy exposure was reported to Brazil's AEFI PV database (SI-PNI AEPV);
- Valid contact information (in SI-PNI AEPV);
- Study participants must provide a signed and dated informed consent form (ICF) or assent form (AF) (based on local regulations), and/or a signed and dated ICF by the parent(s) or other legally acceptable representative (and by an independent witness if required by local regulations) if a minor.*

* Women who meet the inclusion criteria and provide informed consent to participate and complete the structured interview, but who do not consent to medical record review and/or database linkages will still be included in the study; however, their data will be analyzed separately in a sensitivity analysis.

9.2.5.2 **Exclusion criteria**

- Presence of a major language barrier, medical or psychiatric condition that would prevent a woman from providing informed consent or accurate medical or medication/vaccination histories.

9.2.6 **Investigator selection**

The study investigators were selected on the basis of their expertise in pediatrics, maternal and child health, epidemiology and clinical research, as well as their expertise with Brazil's public and health databases and their access to these databases (Appendix 1). In addition, these investigators were recommended by Paraná's Secretary of Health.

9.3 **VARIABLES**

9.3.1 **Primary endpoints**

The primary study endpoints will include all serious and non-serious maternal, pregnancy related, birth outcomes, neonatal and infant events as described below occurring anytime between cohort entry and the end of follow-up for each event. Although formal diagnostic criteria such as those of the Brighton Collaboration are available for a number of the outcomes of special interest, it is unlikely that these are used in routine clinical practice. As such, the diagnoses will be based on clinician assessment as recorded in the medical record and/or databases.

- **Maternal adverse events following immunization:** will be defined as all reported adverse events following immunization (serious and non-serious) occurring *independent of the pregnancy* (e.g., injection site reactions, systemic reactions).

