9.9 STRENGTHS AND LIMITATIONS OF THE RESEARCH METHODS

The most important strength of this study is that, unlike most pregnancy registries that rely on passive reporting, the identification and enrollment of pregnancy exposures will be active. Another important strength is that self-reported vaccination status and outcomes will be verified using medical record review and database linkages; thereby mitigating the risk of recall and reporting bias, a potential danger with retrospectively collected outcomes. Also, offsprings will be followed for up to 12 months post-birth to assess the risk of birth defects that may not be detected at birth, and to assess the risk of hospitalized and/or severe dengue among infants exposed in utero. On the other hand, this study will also have some limitations that need to be considered. First, the baseline dengue serostatus of most exposed pregnant women will not be known as the vaccinations studied occurred before the recent "test and vaccinate" recommendation. As such, should a safety concern arise, it will not be possible to distinguish between vaccine associated dengue in seronegative vaccinees from vaccine failure or waning immunity in seropositive vaccinees. Second, the majority of outcomes will be ascertained retrospectively, thus increasing the risk of recall and detection bias. However, this risk will be, in part, mitigated by the identification of outcomes using multiple data sources, and by the use of a sensitivity analysis stratified according to the nature of the outcomes (i.e., prospective vs. retrospective) if a sufficient number of women can be prospectively enrolled. Third, women who are unreachable, refuse to participate or have died prior to enrollment may be systematically different from study participants and thus, could introduce bias. However, permission will be sought from the Ethics Committee to obtain *aggregate* level information to undertake a comparison of participants and non-participants with regards to baseline characteristics and characteristics of prenatal care to assess the likelihood, strength and direction of such bias. Fourth, although the identification of CYD-TDV exposed pregnant women will be active, the database used to identify these women (SI-PNI EAPV) is part of Brazil's passive AEFI reporting system. As such, some pregnancy exposures may be missed despite educational efforts to stimulate reporting; however, there is no reason to believe that pregnancy exposures captured in the database will be systematically different from those who may be missed. As such, this will impact the precision of the results but not their validity. Fifth, the use of multiple data sources for identifying outcomes may introduce some discordance; however, the impact of this on outcome misclassification will be minimized by choosing *a priori* a gold standard source for each event. Sixth, given the young age of most vaccinees in Paraná, it is possible that many of the pregnancy exposure will be in adolescents; an age group less likely to carry the pregnancy to

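### Maternal events after immunization are a primary endpoint learned mainly from one interview 1 to 4 years after the dose, and the national AEFI database that identifies the women is not used as a source for them

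*Protocol*

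**What the plan says.** Section 9.3.1 defines the maternal endpoint as "all reported adverse events following immunization (serious and non-serious) occurring" independently of the pregnancy, and gives as examples "e.g., injection site reactions, systemic reactions". Primary endpoint events count if "occurring anytime between cohort entry and the end of follow-up for each event", and cohort entry is the first vaccination during the exposed pregnancy (section 9.2.2).

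Section 9.4(i) lists among the items taken from the structured questionnaire "use of recognized teratogenic substances (e.g., alcohol), maternal AEs, pregnancy outcomes, neonatal and infant outcomes". Section 9.4(ii) gives the purpose of medical record review: "To be used to supplement and verify self-reported information". Section 9.1.1 adds contact with the woman's physician or another provider, and makes the medical record the reference for most data when sources disagree. Under section 9.6.1 and Appendix 6, retrospective women are interviewed once.

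For SI-PNI EAPV, section 9.4(iii) states: "This database will be used to identify pregnant women exposed to CYD-TDV in the private and public health care sectors". Its second stated use is "to obtain contact information for these women". Section 9.2.2 lists name, telephone, address and email as the fields to be extracted. Appendix 5 takes one further item from it, gestational age at exposure.

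Section 9.9 counts as a strength that "self-reported vaccination status and outcomes will be verified using medical record review and database linkages".

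**The concern.** Events soon after a dose are hard to establish from an interview held years later. Mild ones may be forgotten, and women whose pregnancies went badly may remember them differently; section 9.8.1 itself warns of recall and reporting bias when outcomes are already known. The protocol relies on multiple sources to limit this. For maternal AEFI, however, none of the linked databases is a named source, and the one set up to receive AEFI reports serves other purposes.

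At stake is how the maternal AEFI frequencies are read. Section 9.7.1 reports maternal outcomes as absolute risks with 95% confidence intervals, over all exposed women in the registry. Those intervals express sampling error only, not incomplete or selective recall. The gap is widest for private-sector women, whose outcome data section 9.7.4 expects to be limited to self-report.

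**Working it through.** **1. Time from dose to interview.** The protocol gives no figure for this. Inputs are the campaign dates in section 7.2 and the enrolment window of July/August 2019 to July 2020 (sections 6 and 9.1.1), taken as 1 July 2019 to 31 July 2020. Where only months are given, I use the first and last day.

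Interval in years = (interview date − dose date in days) / 365.25. Shortest: last campaign day to 1 July 2019. Longest: first campaign day to 31 July 2020.

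| Campaign | Shortest | Longest |
|---|---|---|
| 13 Aug to 23 Sep 2016 | 1011 / 365.25 = 2.77 | 1448 / 365.25 = 3.96 |
| 3 Mar to 7 Apr 2017 | 815 / 365.25 = 2.23 | 1246 / 365.25 = 3.41 |
| Sep to Oct 2017 | 608 / 365.25 = 1.66 | 1064 / 365.25 = 2.91 |
| Mar to Jun 2018 | 366 / 365.25 = 1.00 | 883 / 365.25 = 2.42 |

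A private-market dose on 1 July 2016 would reach 1491 / 365.25 = 4.08 years. A later start of enrolment would lengthen the shortest intervals.

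**2. Could the maternal data be prospective for these campaigns?** Last dose 30 June 2018; latest LMP still counted as exposed, 30 days later, 30 July 2018. Assuming a 280-day term, delivery falls on 6 May 2019, and 42 days of maternal follow-up end on 17 June 2019. That is before enrolment opens. A 42-week pregnancy adds 14 days, to 1 July 2019, the earliest possible opening. Maternal follow-up is therefore over for essentially all campaign exposures already held.

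**3. How many women?** The 214 reports in section 9.5 had been submitted by 19 December 2018. That is 194 days (0.53 years) before 1 July 2019, so all 214 reports, and the doses they concern, precede the first possible interview by at least that long.

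**4. Which source is assigned to maternal AEFI?** From section 9.4 and Appendix 5:

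- Structured questionnaire: maternal adverse events, by self-report.
- Medical records: supplement and check on self-report.
- SISPRENATAL: pregnancy-related outcomes.
- Paraná immunization registry: vaccination dates.
- SINASC: delivery, birth and neonatal outcomes.
- SIM: maternal, neonatal and infant deaths.
- SI-PNI EAPV: identification, contact details, gestational age at exposure.

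Section 9.8.2 names SISPRENATAL, SINASC and SIM as examples of the existing databases to be used and does not name SI-PNI EAPV. Nowhere is SI-PNI EAPV a source or check for adverse events. Yet the inclusion criteria (section 9.2.5.1) require a report in it for every woman, it covers both care sectors, and section 9.4(iii) says all its data can be accessed on request with ethics approval.

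**The case against.** The strongest reply is that the protocol nowhere says SI-PNI EAPV holds these women's reactions. It records pregnancy exposures even without an event, the 214 entries are described as exposure reports, and section 9.9 calls the system passive. How many contain an event or an onset date is unknown; it could be none. This stands: usable content is an assumption, and a reader who infers that the reactions are already recorded there at the time they occurred goes beyond the documents.

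Second, the endpoint is not left to unchecked memory. Provider contact, primary care records and hospital records are planned. That mild reactions seldom reach such records is plausible, but the protocol does not say so. This also stands. It does not supply a database for the endpoint, and section 9.7.4 concedes that private-sector records may be out of reach.

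Third, recall bias is disclosed (sections 9.8.1 and 9.9), and analyses are split by prospective and retrospective status. Disclosure is to the protocol's credit. For campaigns already held, though, the split leaves essentially all maternal data in one stratum.

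Fourth, section 9.9 speaks of records and linkage together, section 9.1.1 makes both subject to availability, and section 9.9 promises a reference source chosen in advance for each event. The sentence on verification is therefore not false; it needs a qualification for this endpoint.

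Finally, table layout can be left to the analysis plan. The fields requested from a database cannot, since no later analysis recovers data never requested.

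**Conclusion.** The point holds as a gap in the choice of data sources. For the campaigns already held, maternal AEFI rest mainly on one interview about 1.0 to 4.0 years after the dose, supplemented by medical records and provider contact where available. No linked database is assigned to them, and the AEFI database in which every eligible woman has a report is not used for adverse events.

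Two stronger readings are tempting. One is that SI-PNI EAPV serves only to find and contact women; Appendix 5 also takes gestational age from it. The other is that the maternal part of the primary objective cannot be answered. Injection-site and systemic reactions are only examples of the endpoint, serious maternal events are included, and the pregnancy-related outcomes in Appendix 2 have other sources. The supportable conclusion is that AEFI frequencies, particularly for non-serious events, will be less reliable than their intervals suggest.

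The gain from the change depends on how many reports contain event content, which the protocol does not say. It is worth making because it adds a source independent of late recall, including for private-sector women.

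**What to change.** - **Sections 9.4(iii) and 9.2.2:** add to the SI-PNI EAPV request any adverse-event content of each participant's report (event, onset date, seriousness). Name it as a supplementary source and check for maternal AEFI, alongside medical records and interview.
- **Reporting:** show maternal AEFI by source, with events known only from the interview identified as such.
- **Section 9.9:** state that, of the linked databases, only SI-PNI EAPV can support this endpoint, and that it is passive and includes exposure-only reports.

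The cost is a slightly larger data request under an ethics approval that is needed anyway, and a breakdown by source in the tables. The content could be used only for women who agree to database linkage. The change may add few events if most reports record exposure alone.

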9.5 SAMPLE SIZE

Ultimately, the sample size will depend on the number of pregnant women who were inadvertently exposed to CYD-TDV during Paraná's public vaccination campaigns, had this exposure reported to the SI-PNI AEPV database during the study's enrollment period, and provide signed informed consent. As such, every effort will be made to recruit all eligible women. As of 19 December 2018, 214 reports of inadvertent pregnancy exposures had been submitted to the SI-PNI-AEPV reporting system. However, this number could increase if additional vaccinations campaigns are offered during the study enrollment period.

Based on published estimate, adverse pregnancy outcomes such as spontaneous abortions are expected to occur at a frequency of 1/7 (14.3%), low birth weight at 1/12 (8.3%), fetal death/stillbirth at 1/200 (0.5%).⁸ Birth defects occur in 1/135 (0.007) pregnancies for genital and urinary tract defects.⁹ In Brazil, microencephaly occurs at a frequency ranging from 0.0 to 20.32 per 10,000 live births, depending on

the region.¹⁰ Ultimately, the level of precision (expressed as 95% CI) for the observed point estimates will depend on the number of identified women exposed during pregnancy who consent to participate in the pregnancy registry:

Participation rate	Expected number of exposed pregnancies	Expected observed rate (%)	Number of outcomes	Expected 95% CI
100%	214	14.486%	31	(10.06; 19.93)
		8.411	18	(5.06; 12.97)
		0.467	1	(0.01; 2.58)
75%	160	14.375	23	(9.34; 20.78)
		8.125	13	(4.4; 13.49)
		0.625	1	(0.02; 3.42)
50%	107	14.019	15	(8.06; 22.07)
		8.411	9	(3.92; 15.37)
		0.935	1	(0.02; 5.1)

9.6 DATA MANAGEMENT

9.6.1 Data collection process and schedule

Study investigators or their delegate will collect study data obtained from the structured interviews and the review of medical records; these data will be entered by the investigators or their delegate into an electronic data capture (EDC) system. Record linkages for data extracted from the various study databases will be carried out either by the DoH or the study investigators (depending on availability of qualified personnel) and all study databases will be stripped of nominal data after successful linkage and replaced by the participant's unique, anonymized study identification number.

The primary data collected during the study will be managed using two different platforms depending on whether or not they pertain to an AE. Clinical data, defined as all primary data recorded in the electronic case report form (eCRF), will be managed by the Sponsor's Clinical Data Management (CDM) platform or by authorized representative (e.g., Clinical Research Organization [CRO]). In addition, all data pertaining to AEs that are reported by the Investigators on an individual case safety report (ICSR) form will also be transferred to the Sponsor's Pharmacovigilance (PV) database (AGEIS) managed by the Sponsor's Global Pharmacovigilance (GPV) Department. On the other hand, data extracted from the MoH and DoH's databases will be maintained separately in their original electronic format.

During the study, clinical data recorded in the eCRF will be integrated into the study database under the responsibility of the Sponsor's CDM platform. Data monitoring and quality control in the form of computerized logic and/or consistency checks will be systematically applied to detect errors or omissions. In addition, data reviews may be performed by the Sponsor or representative throughout the course of the study. Questions pertaining to data from primary data sources will be submitted to the investigators or their delegate for resolution using the EDC system. Each step of this process will be monitored through the implementation of individual passwords to

control access to the study database to ensure data integrity. After integration of all corrections in the primary data dataset, and after AE information available from CDM and the GPV Department has been reconciled, the primary data database will be released for statistical analysis. Review of the data from primary data sources is anticipated to take place through the data review process led by Data Management.

For women and offsprings enrolled retrospectively (i.e., outcomes occurred prior to study enrollment), their primary data will be obtained all at once (i.e., one interview) owing to the retrospective nature of the data; however, it may be necessary to contact the mother/legal guardian post-interview for clarification purposes. For women and offsprings enrolled prospectively (i.e., outcomes occurring after enrollment), the data will be collected at pre-specified time points during pregnancy (at enrollment, 1st, 2nd and 3rd trimester). For outcomes in the offsprings, data will be collected within 3 months (± 1 month) of birth, then at 6 months (± 1 month) and 12th months (± 1 month) post-delivery.

Details of the data to be collected and the data collection schedule can be found in Appendix 6.

